10.4 Data Analysis Plans

10.4.1 Primary Objective: To describe the safety, as determined by the rate of Grade ≥ 3 non-hematologic AEs and treatment-related mortality, of a risk-adjusted approach to the treatment of MCD with rituximab (375 mg/m² weekly for four weeks) +/- etoposide (100 mg/m² weekly for four weeks) in Malawi.

The rate will be estimated for individual AEs and a summation of Grade ≥ 3 non-hematologic AEs will be estimated along with a 95% confidence interval.

The rate of treatment-related mortality will be estimated along with a 95% confidence interval around the point estimate.

10.5 Secondary Objectives

10.5.1 To better characterize MCD presentation in Malawi.

Basic demographics and baseline laboratory values will be summarized using descriptive statistics (i.e., means, medians, and variability measures for continuous variable; rates and proportions for binary variables).

10.5.2 To describe the efficacy of the risk-adjusted approach as determined by clinical and radiologic response rates, 90-day, one-year, and two-year EFS and OS.

An event for EFS is either relapse (defined as “MCD attack” in the Inclusion Criteria (section 4.1)), refractory disease, lost-to-follow-up (LTFU), or death. We will consider patients LTFU if they cannot be contacted by phone for three months. Given the high mortality associated with MCD and previously published literature supporting a strong association between LTFU and mortality in SSA, we will consider LTFU as a failure event for both EFS and OS.⁴³ Relapse for purposes of this study will be defined as recurrence of an “MCD attack” (Inclusion Criteria; section 4.1) requiring re-initiation of treatment, with a strong preference for biopsy-proven recurrence whenever possible. We will conduct survival analysis using Kaplan-Meier methods. Radiologic response will be assessed in parallel with clinical response with response criteria defined in section 7.1.7. We will assess the prognostic value of radiologic response for EFS and OS in Cox proportional hazards model.^{10,15,16}

10.5.3 To describe the safety, as determined by the rate of all AEs during a risk-adjusted approach to treatment of MCD in Malawi.

All AEs will be described up to 30 days after final dose of MCD-directed treatment.

10.5.4 To describe the rate of KS exacerbation, as defined by symptomatic or clinical (dermatologic or visceral organ) exacerbation of disease.

The rate of KS exacerbation will be reported as the number of KS cases requiring KS-specific treatment divided by the number of patients with pre-existing KS (as defined by personal history of KS, baseline presence of KS, or KS in lymph node biopsy). This will be estimated along with a 95% confidence interval for the proportion.

10.5.5 To describe the quality of life of patients with MCD before, during and after treatment with a rituximab-based, risk-adjusted treatment approach, as assessed by the MCD symptom score⁴² and PROPr instrument.⁴⁴

The MCD symptom score will be summed and differences across treatment will be compared using a paired t-test. We hypothesize that quality of life will be significantly improved from baseline to end of treatment with rituximab-based treatment (the MCD symptom score will be lower and PRO-Pr will be higher in utility).

10.5.6 To describe the trends in hemoglobin, platelet count, CRP, IL-6, IL-10, and KSHV viral load before, during, and after treatment with a risk-adjusted, rituximab-based treatment for MCD in Malawi, and to describe the utility of these markers as a predictor of relapse.

Hemoglobin, platelet count, CRP, IL-6, IL-10, and KSHV viral load will be measured at baseline, day 15, and end-of-treatment. Differences will be compared by paired t-test. We hypothesize that hemoglobin, platelet count, CRP, and plasma KSHV viral load will be strongly associated with disease activity (hemoglobin and platelet count will increase in remission and CRP and KSHV viral load will decrease in remission).

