1.0 BACKGROUND AND RATIONALE

1.1 Study Synopsis

In sub-Saharan Africa (SSA), Kaposi sarcoma herpesvirus (KSHV)-related cancers account for 10-35% of malignancies¹⁻³ and >10% of cancer-related deaths.³ Multicentric Castleman disease (MCD) is a life-threatening lymphoproliferative disorder characterized by systemic inflammation and lymphadenopathy. MCD is strongly associated with KSHV and human immunodeficiency virus (HIV). KSHV seroprevalence in SSA is >40%,^{4,5} the highest of any region in the world; likewise, the prevalence of HIV is high.⁶ Substantial knowledge gaps remain regarding treatment for MCD, including outcomes, safety, and cost-effectiveness, particularly in SSA.

MCD can be controlled with chemotherapy. When chemotherapy is discontinued, however, rapid relapses or development of non-Hodgkin lymphoma (NHL) occur with high mortality.^{7,8} Long-term remission is achieved in most patients with rituximab, an anti-CD20 monoclonal antibody, as described in small clinical trials in high-income countries (HIC).⁹⁻¹¹ However, rituximab has not been evaluated for MCD in SSA, nor are there published safety data for rituximab from the region.

In this study, we aim to determine the safety and efficacy of first-line, risk-stratified rituximab-based MCD treatment in Malawi in a single-arm, phase II clinical trial. We will enroll 27 subjects with newly diagnosed or previously treated MCD (who have not previously received rituximab) requiring treatment (B symptoms or hemoglobin <10 g/dL).¹² Subjects will be treated with four weekly doses of rituximab. High-risk subjects (defined as patients with Eastern Cooperative Oncology Group (ECOG) performance status >2 or hemoglobin <8 g/dL)^{9,10,13-16} will also receive etoposide chemotherapy.^{9,11} Subjects will be followed for one year for toxicity and two years for survival. The primary outcome will be safety, defined as the frequency of \geq Grade 3 treatment-related Common Terminology Criteria for Adverse Events (AEs). Secondary outcomes will be event-free survival (death, progression, or development of NHL) and 1- and 2-year overall survival (OS). We also aim to compare the cost-effectiveness of first-line rituximab treatment for MCD in Malawi to chemotherapy (using our historical controls).

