3.2 Secondary Endpoints

3.2.1 At study entry, basic demographics and baseline laboratory values will be summarized using descriptive statistics (i.e., means, medians, and variability measures for continuous variable; rates and proportions for binary variables). Screening assessments to be completed within 21 days prior to study enrollment.

3.2.2 Overall survival will be assessed at 12 weeks, one year, and two years from the start of treatment.

3.2.3 Event-free survival will be defined as the rate of refractory disease, relapse (same definition of active disease as in the inclusion criteria in section 4.1), non-Hodgkin lymphoma development or death and will be assessed at 12 weeks, one year, and two years from the start of treatment.

3.2.4 Clinical response rate at end of treatment and 12 weeks from treatment initiation (clinical response defined as resolution of presenting signs/symptoms that defined

the Multicentric Castleman disease (MCD) attack) without relapse at 12 weeks. MCD attack/flare is defined in Section 4.1.1.

3.2.5 Radiologic response rate is the percentage of patients without relapse at end of treatment and 12 weeks from treatment initiation. Chest radiography and abdominal sonography will be used for staging. Per Revised response criteria for gross lymphadenopathy, response will be evaluated via complete survey of lymph nodes with measurements and physical assessment of other palpable masses with measurements.

Response criteria for lymph node response will be as follows: Complete response (CR)- disappearance of all evident disease; Partial response (PR)-at least 50% decrease in target lesions with no increase in non-target lesions, Stable disease (SD)- Neither sufficient shrinkage to qualify for PR nor sufficient increase to qualify for progressive disease (PD); PD- appearance of a new lesion or at least a 50% increase in lesion size.

3.2.6 Additional safety assessment will be graded by CTCAE v 5.0 through 12 weeks from the start of therapy.

3.2.7 Kaposi sarcoma exacerbation will be defined as new symptoms attributed to KS or clinically evident exacerbation of dermatologic or visceral disease. All disease flares will be biopsy confirmed whenever possible.

3.2.8 Quality of life will be assessed by the MCD symptom score, a patient-reported outcomes questionnaire, and PROMIS Global 10, at baseline (week 1), 15 days (week 3), end of treatment (week 5), 12 weeks, 6 months, and 24 months after treatment, and at the time of any relapse.

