5.0 TREATMENT PLAN

5.1 Schema

[figure not shown]

Figure 4. Clinical trial schema for newly diagnosed patients with MCD requiring treatment.
"High-risk disease" defined as ECOG performance status >2 or hemoglobin <8 g/dL.

Clinical trial schema for newly diagnosed patients with MCD requiring treatment.

¹ "High-risk disease" defined as ECOG performance status >2 or hemoglobin <8 g/dL at the time of screening or enrollment labs. Note that a patient receiving a blood transfusion due to hemoglobin <8 g/dL within 1 month of enrollment will be considered high-risk.

² See Time and Events Table (8.1) for detailed study visit components.

³ MCD-SS=MCD symptom score

We will conduct a single arm, phase II clinical trial for safety and efficacy of risk-stratified treatment with rituximab +/- chemotherapy for MCD. Eligible patients will be enrolled and treated according to the study schema. High-risk patients (defined as patients with ECOG performance status >2 or hemoglobin <8 g/dL at the time of screening or enrollment labs)^{9,10,13-16} will receive four weekly doses of rituximab (375 mg/m²) and etoposide (100 mg/m²) as in Bower, et al.⁹ Low-risk patients will receive the same dose of rituximab alone.

The planned sample size is 27 patients and the primary outcome is safety. Secondary outcomes include one- and two-year EFS (combination of relapse, development of NHL, or death), OS, and KS exacerbation rates.

We will also collect clinical, laboratory, virologic data, and stored samples at baseline and end-of-treatment to both describe the presentation of MCD in our population and to evaluate risk factors for death or relapse.

Finally, we will conduct comprehensive microcosting analysis and a Markov model cost-effectiveness analysis.

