7.1.6 Clinical Disease Assessment

Response assessment varies across MCD studies, but our clinical response will be defined as follows:

Event-free survival will be defined by the absence of an event. An event includes either: relapse of symptomatic MCD requiring re-initiation of treatment as in the previous study by Bower, et al, death, or progression to non-Hodgkin lymphoma.¹⁰ Definition of symptomatic MCD for purposes of this study are the same as in the “Inclusion Criteria” (Section 4.1).

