10.0 STATISTICAL CONSIDERATIONS

10.1 Study Design/Study Endpoints

This is a single arm, prospective, phase II clinical trial for safety and efficacy of risk-stratified treatment with rituximab +/- chemotherapy for MCD. Eligible patients will be enrolled and treated according to the study schema. High-risk patients (defined as patients with ECOG performance status >2 or hemoglobin <8 g/dL during screening or enrollment)^{9,10,13-16} will receive four weekly doses of rituximab (375 mg/m²) and etoposide

(100 mg/m²) as in Bower, et al.⁹ Note that patients with low hemoglobin within the last month that receive a blood transfusion as treatment will be considered high risk if their pre-transfusion hemoglobin was <8 g/dL. Low-risk patients will receive the same dose of rituximab alone. The planned sample size is 27 patients and the primary outcome is safety. Secondary outcomes include one- and two-year EFS (relapse, development of NHL, or death), OS, and KS exacerbation rates. We will also collect clinical, laboratory, virologic data, and stored samples at baseline and end-of-treatment to both describe the presentation of MCD in our population and to evaluate risk factors for death or relapse. Finally, we will conduct comprehensive microcosting analysis and a Markov model cost-effectiveness analysis.

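### Section 10.5 leaves NHL out of the EFS events and counts KS exacerbation only when KS needs treatment, which departs from the plan's own definitions of both secondary endpoints

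*Combined protocol and SAP*

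**What the plan says.** **EFS.** Six places in the protocol state what counts as an EFS event.

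- 1.1 Study Synopsis: "event-free survival (death, progression, or development of NHL".
- 3.2.3: "refractory disease, relapse (same definition of active disease as in the inclusion criteria in section 4.1), non-Hodgkin lymphoma development or death".
- 5.1 Schema: "one- and two-year EFS (combination of relapse, development of NHL, or death".
- 7.1.6: "relapse of symptomatic MCD requiring re-initiation of treatment", together with "death, or progression to non-Hodgkin lymphoma".
- 10.1: "one- and two-year EFS (relapse, development of NHL, or death".
- 10.5.2, the section that specifies the analysis: relapse in the sense of an attack of multicentric Castleman disease (MCD), "refractory disease, lost-to-follow-up (LTFU), or death". It further qualifies relapse as "requiring re-initiation of treatment, with a strong preference for biopsy-proven recurrence whenever possible".

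Section 10.5.2 explains why loss to follow-up (LTFU) is treated as failure for EFS and OS. It gives no reason for leaving NHL out.

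**KS.** Objective 2.2.7, endpoint 3.2.7 and the heading of 10.5.4 all describe exacerbation as worsening that shows as symptoms or on clinical assessment, in skin or viscera. None of them makes treatment a condition. The calculation under 10.5.4 then takes as numerator only KS that calls for KS-directed therapy. The denominator is the patients with pre-existing KS, identified by history, by presence at baseline or in the node biopsy. A 95% confidence interval for the proportion is planned.

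**The concern.** An analyst who programs EFS and the KS rate from 10.5 obtains quantities that differ from those the endpoint section defines.

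For EFS, NHL is one of the outcomes the treatment is meant to prevent: section 1.3 cites a reduced NHL risk in support of rituximab. Under 10.5.2, NHL alone would not count against the regimen. A patient with NHL who later dies would enter the Kaplan-Meier curve at death and not at diagnosis. The same event definition feeds the Cox model that relates radiologic response to EFS.

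For KS, exacerbation is a recognised risk of rituximab: section 1.3 gives 36-75% for monotherapy and section 1.4 gives 9/24 (38%) for a risk-adapted regimen. Counting only treated cases can make the regimen look safer on this outcome than 3.2.7 would show.

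If the conflict remains at analysis, someone must choose between definitions after the data are known.

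**Working it through.** **Is a plan figure affected?** The plan gives no numerical target for EFS or KS. Its only design calculation is the primary safety test in 10.2: 24 patients, safe if at most 6 events, null rate 0.40, expected rate 0.20, one-sided alpha 0.10. The exact binomial gives P(X ≤ 6 | 24, 0.40) = 0.096 and P(X ≤ 6 | 24, 0.20) = 0.811. Enrolment is 24/0.9 = 26.7, rounded up to 27. These agree with the stated 0.1, 80% and 27, and nothing below alters them.

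**EFS event lists side by side.**

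| Section | Relapse | Refractory | NHL | Death | LTFU |
|---|---|---|---|---|---|
| 1.1 | says progression | no | yes | yes | no |
| 3.2.3 | yes | yes | yes | yes | no |
| 5.1 | yes | no | yes | yes | no |
| 7.1.6 | yes, if treatment restarted | no | yes | yes | no |
| 10.1 | yes | no | yes | yes | no |
| 10.5.2 | yes, if treatment restarted | yes | **no** | yes | yes |

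NHL is in five of six lists and absent only from the one that governs the analysis. The wording of 10.5.2 presents its list as complete. Relapse there means a recurrent MCD attack, which is a different diagnosis from NHL. The table also shows that the other five lists disagree with one another: 5.1, 7.1.6 and 10.1 lack refractory disease, and 1.1 uses a different term.

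**Size for EFS.** Suppose all 27 enrolled patients are analysed, none is censored before the time point, and the other events are fixed. If m patients have NHL and no other listed event by then, EFS under 10.5.2 exceeds EFS under a list with NHL by m/27.

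- m = 1: 1/27 = 3.7 points.
- Illustration with an assumed 6 other events and m = 2: 1 − 6/27 = 77.8% against 1 − 8/27 = 70.4%, a gap of 7.4 points.
- If only 24 patients were analysed, for example because the evaluability rule in 8.4 were applied, one case would be 1/24 = 4.2 points.

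Timing, with assumed dates: NHL at month 10 and death at month 14. Under 3.2.3 the event falls at month 10 and the patient has failed at one year. Under 10.5.2 the patient is event-free at one year and fails at month 14, a shift of 14 − 10 = 4 months.

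**Size for KS.** Let k be the number of patients with pre-existing KS (not given, at most 27), E the number of them who meet 3.2.7, and a the number of those E who need no KS-directed treatment. Assume that nobody is treated for KS without meeting 3.2.7.

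- Rate with the 3.2.7 numerator: E/k.
- Rate as calculated in 10.5.4: (E − a)/k.
- Difference: −a/k, or 1/k per patient. This is 3.7 points at k = 27, 8.3 at k = 12 and 12.5 at k = 8.

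Illustration with assumed k = 12, E = 6, a = 3: 6/12 = 50% (exact 95% CI 21-79%) against 3/12 = 25% (5-57%).

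**The case against.** The strongest reply is that this is a slip of the pen. Section 10.1, in the same statistical chapter, names NHL, as do four other places, and no test or threshold hangs on EFS. That stands as to intent. A reader might infer that the sponsor chose to drop NHL, and the documents do not support that. The slip nevertheless sits in the section an analyst would program from, and no other listed event reliably captures NHL at its date of onset.

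Several stronger readings are tempting and should not be drawn.

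- *The NHL effect is large.* The 15-25% in section 1.5 refers to patients treated with chemotherapy. The documents give no expected NHL count under rituximab, so only a per-case figure can be stated.
- *The relapse definitions conflict sharply.* Section 3.2.3 refers to 4.1, and 4.1.7 already requires that treatment be indicated. What remains is the difference between treatment indicated and treatment restarted. That is worth aligning but narrow.
- *Counting LTFU as failure is a hidden change.* Section 10.5.2 states and justifies it, and a statistical section is a normal place for such a rule. No defect is claimed.
- *12 weeks against 90 days.* The labels differ, but no defect is claimed.
- *New KS in patients without pre-existing KS inflates the 10.5.4 rate.* The section reports a proportion over patients with pre-existing KS, so the natural reading is that the numerator is a subset of them.

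One further reply on KS has force: 3.2.7 states no denominator, so the comparison above borrows the one in 10.5.4. The mismatch in the numerator does not depend on that choice.

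**Conclusion.** The point holds. Section 10.5.2 omits an EFS event that every other definition includes, and 10.5.4 counts something narrower than its own heading, 2.2.7 and 3.2.7.

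For EFS, with the other events fixed and follow-up complete to the time point, the omission can only leave the estimate equal or higher, by 3.7 points per uncounted case on 27 patients. With censoring that per-case figure is approximate. A case that is merely dated late can also fall on a smaller risk set, so the direction is strictly guaranteed only without censoring. Because LTFU counts as failure, censoring before 24 months should be limited.

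For KS, with the denominator of 10.5.4 and no treatment given outside 3.2.7, the reported rate can only equal or understate the defined rate, by 1/k per untreated exacerbation, with k unknown.

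The number of patients affected cannot be predicted from the documents. Both endpoints are descriptive and secondary. A reader might infer that the trial's main safety conclusion is at risk, but it is not: neither item enters the primary test or its sample size. The correction should be made before analysis.

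**What to change.** **EFS.** Add development of NHL to 10.5.2. Then use one event list in 1.1, 3.2.3, 5.1, 7.1.6, 10.1 and 10.5.2: the first of refractory disease, relapse, NHL, death, or LTFU under the existing 10.5.2 rule. Changing 10.5.2 alone would leave 5.1, 7.1.6 and 10.1 without refractory disease. Use one wording for relapse throughout; whether it requires treatment to be restarted is for the sponsor to reconcile. The visible text does not define refractory disease, so a one-line definition should accompany the list.

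**KS.** In 10.5.4, take as numerator the patients with pre-existing KS who meet 3.2.7, over all patients with pre-existing KS as now defined there. Report KS needing KS-directed treatment as a separate, labelled proportion. Report any new KS in patients without pre-existing KS separately as a count.

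**Cost.** Wording in the six EFS places and in 10.5.4, plus one extra proportion and one count. The existing endpoints already call for data on NHL, KS exacerbation and KS treatment. There is no change to sample size, visits or the primary analysis.

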5.8 Duration of Follow Up

For determination of study endpoints, all subjects will be followed for up to 24 months or until death, whichever occurs first after removal from study treatment.

Subjects removed from study treatment for unacceptable AEs will be followed for resolution or stabilization of the AE(s). All subjects (including those withdrawn for AEs) should be followed after removal from study treatment as stipulated in the protocol.

Although study follow-up is for 24 months, patients will be consented to be contacted at 30, 36, 42, 48, 54, and 60 months simply to assess vital status after completion of study procedures.

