10.2 Sample Size, Accrual and Duration of Accrual

To assess safety, toxicities will be monitored, graded, and documented by investigators at each clinic visit. Rituximab-based treatment will be considered safe in this population provided <40% non-hematologic AEs; we hypothesize that the true rate will be around 20%, based on previous studies.^{9,10,15,16} With a sample size of 24 patients, we reach 80% power to reject (if we observe $\leq 6 \geq$ Grade 3 AEs) the null hypothesis (H_0 : toxicity rate $>40\%$) using a one-sided exact test at $\alpha=0.1$. To account for 10% possible loss to follow-up during the toxicity-monitoring period, we will plan to enroll 27 patients. We plan to enroll approximately 10 patients annually and therefore expect to accrue patients for a total of three years.

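### The rule counting lost phone contact as an OS and EFS failure has no failure date, no reversal and no censored sensitivity analysis, so failures can include living patients

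*Combined protocol and SAP*

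**What the plan says.** Section 10.5.2 defines loss by phone alone: "We will consider patients LTFU if they cannot be contacted by phone for three months". It then says "we will consider LTFU as a failure event for both EFS and OS". The reason given is the high mortality of multicentric Castleman disease (MCD) and "previously published literature supporting a strong association between LTFU and mortality in SSA", with a citation. The estimator follows: "We will conduct survival analysis using Kaplan-Meier methods".

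On timing, section 3.2.2 says "Overall survival will be assessed at 12 weeks, one year, and two years from the start of treatment"; section 10.5.2 calls the first time point 90 days.

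The trial has other ways of learning that a patient is alive. The Time and Events Table (section 8.1) has survival assessed at every visit, with long-term visits every three months to month 24. Section 5.8 adds that "patients will be consented to be contacted at 30, 36, 42, 48, 54, and 60 months simply to assess vital status".

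Section 3.2.3 defines EFS through refractory disease, relapse, "non-Hodgkin lymphoma development or death and will be assessed at 12 weeks, one year, and two years from the start of treatment". Section 7.1.6 lists relapse, death and progression to lymphoma. Neither mentions LTFU.

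The only loss rate in the plan is in section 10.2: "To account for 10% possible loss to follow-up during the toxicity-monitoring period", 27 patients are enrolled to give 24.

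**The concern.** A Kaplan-Meier analysis needs a date for every event. For an LTFU failure the plan gives none: it could be the last contact or the day on which the three silent months end. The plan is also silent on three related matters: whether a clinic visit counts as contact, what happens when a lost patient is later found alive, and how the estimates look with LTFU censored.

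At stake is what the reported OS means. If some failures are living patients, the figure is no longer overall survival as normally understood, and two analysts could draw different curves from the same data. The EFS event lists add to this, because following section 3.2.3 or 7.1.6 instead of 10.5.2 gives a different set of events. Section 10.5.2 also puts EFS and OS into Cox models for radiologic response, which would use the same undefined events and times.

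**Working it through.** **1. The plan's own figures.** The plan states no sample size, power, target or expected LTFU rate for OS or EFS. Its only design calculation is for the safety endpoint (section 10.2), and it reproduces: P(X ≤ 6 | n = 24, p = 0.40) = 0.0960, within the one-sided 0.10; P(X ≤ 6 | n = 24, p = 0.20) = 0.811, against a stated 80%; 24/0.9 = 26.7, so 27. The LTFU rule does not enter it.

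**2. Size per patient.** Let N = 27 (section 10.2), D = deaths, and L = patients counted as failed through LTFU but in fact alive.
- Two-year OS with LTFU as failure: (N − D − L)/N.
- Two-year OS with true status known: (N − D)/N.
- Difference: L/N. For L = 1 this is 1/27 = 3.7 points; for L = 3 it is 3/27 = 11.1 points.

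L = 3 is an illustration, using the allowance in section 10.2 (27 − 24 = 3; 10% of 27 is 2.7). The same arithmetic applies to EFS for a lost patient who would have stayed event-free.

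**3. Worked illustration (D and L assumed).** N = 27; D = 5, at months 1, 3.75, 6.5, 9.25 and 12; L = 3, all alive, last reached at months 4.5, 12 and 19.5. Two-year OS is:
- LTFU as failure: 19/27 = 70.4%.
- LTFU censored at last contact: (25/27) × (21/24) = 81.0%. Two deaths occur before the first censoring; three more occur with 24 at risk.
- True status: 22/27 = 81.5%.

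Had all three lost patients died, the truth would be 19/27 = 70.4%. The failure rule would then be right, and censoring would overstate survival by about 10.6 points.

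**4. The missing date, first landmark.** Three months is about 91 days. The landmark is day 84 (12 × 7) or day 90.
- Dated when the rule is met, the earliest LTFU failure for a patient reached on day 1 is day 1 + 91 = day 92. None falls inside the window.
- Dated at last contact, every loss before the landmark falls inside it. A patient last reached at the day-22 dose fails on day 22, against about day 22 + 91 = 113 under the other reading.
- With three early losses the estimate moves by 0 or by 3/27 = 11.1 points, on the date alone.

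**5. The missing date, later landmarks.** With 5 deaths by month 9 and 3 patients last reached between months 10 and 11.5 (assumed), one-year OS is 19/27 = 70.4% if dated at last contact. It is 22/27 = 81.5% if dated when the rule is met (months 13 to 14.5). By two years both give 70.4%. So at one and two years the date matters only for patients last reached in the three months before the landmark.

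**6. EFS events by section.**

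| Event | 3.2.3 | 7.1.6 | 10.1 | 10.5.2 |
|---|---|---|---|---|
| Relapse | yes | yes | yes | yes |
| Death | yes | yes | yes | yes |
| Refractory disease | yes | no | no | yes |
| Lymphoma | yes | yes | yes | no |
| LTFU | no | no | no | yes |

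**The case against.** The strongest defence is that the rule is deliberate. It is prespecified and reasoned, and at a common date it can only lower OS and EFS compared with censoring, which is the cautious direction in a single-arm trial. Censoring has the opposite fault: if lost patients have died, it overstates survival. Which error is larger depends on a source that cannot be examined here. All of this stands, and it is why the rule should be kept. It does not supply a date, a rule for reappearance or a single EFS definition. By its title in the reference list, the cited source concerns children with lymphoma in Malawi, whereas this trial enrols adults with MCD; that favours showing both analyses.

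Two limits on the size also stand. The 10% in section 10.2 is an allowance for the toxicity period, not a forecast of loss under the phone rule. And 27 may not be the denominator: section 8.4 restricts efficacy evaluability to patients with measurable disease who were dosed and re-evaluated, so a patient lost early may not be counted at all.

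A reader might infer three stronger points that the documents do not support.
- That the survival figures will include patients known to be living. No section says a patient known to be alive stays a failure; the plan is silent. Counting a patient who attends visits as dead takes a very literal reading of the phone rule, given that survival is assessed at each visit.
- That the results cannot be compared with the historical figures in section 1.5 (two-year OS 42% with chemotherapy; one-year EFS 10% and 78% in Malawi). The documents do not say how loss was handled there, so comparability is unknown. Section 10.5.2 plans no test against those figures.
- That the failure and censored versions bracket the truth. In step 3 they give 70.4% and 81.0% against a true 81.5%. With all three patients censored before any death, the censored figure is 19/24 = 79.2%, further below the truth.

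Section 3.2.2 lists OS time points without defining the event, so it does not contradict section 10.5.2. The direct conflict is among the EFS definitions.

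**Conclusion.** The point holds in this form: as written, section 10.5.2 can count as OS or EFS failures patients who are, or later prove to be, alive, and it leaves the failure date open. The size is 3.7 points per such patient and about 11 points for three, assuming a denominator of 27 and taking three from the section 10.2 allowance purely as an illustration. If every lost patient has died, this understatement is zero. The date alone decides whether early losses count at 12 weeks or 90 days; later its effect is confined to patients last reached in the three months before the landmark. The EFS event lists conflict regardless of any numbers.

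These are secondary endpoints with no stated power or decision threshold. The primary safety analysis and the sample size are unaffected. The plan should still be corrected before the survival analysis, because every gap can be closed with information the trial already plans to collect.

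**What to change.** Keep the LTFU-as-failure analysis and amend section 10.5.2 as follows:

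- (a) Define LTFU as no contact of any kind (phone, clinic visit or record) for three months.
- (b) Date the failure at the last day the patient was known to be alive.
- (c) Remove the OS failure when later contact, including the month 30 to 60 contacts in section 5.8, shows that the patient was alive. This is limited to OS because vital status alone does not show freedom from relapse or lymphoma.
- (d) Report OS and EFS with LTFU censored at last contact alongside, as a sensitivity analysis, without claiming that the two versions bracket the truth.
- (e) Use one EFS definition in sections 3.2.3, 7.1.6, 10.1 and 10.5.2, stating explicitly whether LTFU, lymphoma and refractory disease are events.

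The cost is wording and one extra Kaplan-Meier run per endpoint, with no new patients or data. The small downside is that two survival figures are reported for each endpoint instead of one.
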